8.5 SAFETY OVERSIGHT

Safety data will be reviewed by the study Independent Data Monitoring Committee (IDMC) approximately every 6 months (after first randomized subject started Dara SC administration). The IDMC will no longer review study data after the primary PFS analysis has been completed.

9 CLINICAL MONITORING

Clinical site monitoring will be conducted to ensure that the rights and well-being of human subjects are protected, that the reported study data are accurate, complete, and verifiable, and that the conduct of the study complies with the currently approved protocol, with GCP, and with applicable regulatory requirements.

Monitoring for this study will be performed by a Contract Research Organization (CRO).

Details of clinical site monitoring are documented in a Clinical Monitoring Plan (CMP). The CMP describes in detail who will conduct the monitoring, at what frequency monitoring will be done, at what level of detail monitoring will be performed, and the distribution of monitoring reports.

Independent audits may be conducted to ensure monitoring practices are performed consistently across all participating sites and that monitors are following the CMP.

10 STATISTICAL CONSIDERATIONS

10.1 STATISTICAL AND ANALYTICAL PLANS

The primary analysis of PFS will be performed when the targeted number of PFS events required has been reached. Analysis will use response or progression status as derived by a validated computer algorithm in accordance with modified IMWG response criteria.

10.2 STATISTICAL HYPOTHESES

The primary efficacy endpoint is PFS as assessed by the computer algorithm.

The distribution of PFS will be estimated using the Kaplan-Meier method. The median PFS, along with 95% CIs, will be presented by treatment group. The primary efficacy analysis will be the comparison of the distribution of PFS between the 2 treatment groups using a stratified log-rank test at one-sided 2.5% level of significance, i.e.,

$$H_0: S_{\text{DaraPomDex}}(t) = S_{\text{PomDex}}(t)$$

will be tested against the one-sided alternative hypothesis

$$H_{a1}: S_{\text{DaraPomDex}}(t) > S_{\text{PomDex}}(t) \text{ for all } t \text{ with strictly inequality for some } t.$$

where $S_{\text{DaraPomDex}}(t)$ is the survival distribution function of PFS in the DaraPomDex, and $S_{\text{PomDex}}(t)$ is the survival distribution function of PFS in the PomDex arm. A stratified Cox proportional hazard model will be used to estimate the HR of PFS, along with 95% CI (see [Section 10.4.2](#)).

The primary analysis will be performed when at least 188 PFS events have been documented.

10.3 ANALYSIS DATASETS

Intent-to-Treat Analysis Set

The intent-to-treat (ITT) Analysis Set comprises all subjects to whom study treatment has been assigned by randomization. Subjects who already began treatment with daratumumab for IV infusion (Dara IV) prior to Amendment 1 approval will be offered the option to switch to SC dosing through study end, and they will be included as part of the ITT population.

Safety Analysis Set

The safety analysis set consists of all subjects who received at least 1 dose of study medication. Subjects who have been randomized and did not take at least 1 dose of study medication will not be included in the safety set. Subjects will be analyzed according to the study treatment they actually received.

Pharmacokinetic Analyses

Pharmacokinetic analyses will be performed on the pharmacokinetic-evaluable population, defined as subjects who have received 1 dose of daratumumab and have at least 1 postdose pharmacokinetic sample. All serum concentrations below the lowest quantifiable concentration or missing data will be labeled as such in the concentration data presentation. Concentrations below the lowest quantifiable concentration will be treated as zero in the summary statistics. All subjects and samples excluded from the analysis will be clearly documented in the study report.

Descriptive statistics will be used to summarize daratumumab serum concentrations at each sampling time point and pharmacokinetic parameters of daratumumab such as C_{\min} and C_{\max} .

If sufficient data are available, then population pharmacokinetic analysis of serum concentration-time data of daratumumab may be performed using nonlinear mixed-effects modeling and may include data from other clinical studies. If the population pharmacokinetic analysis is conducted, then details will be given in a population pharmacokinetic analysis plan and the results of the analysis will be presented in a separate report.

Immunogenicity Analyses

The incidence of antibodies to daratumumab (immunogenicity) and rHuPH20 will be summarized separately for all subjects who receive a dose of daratumumab and have appropriate samples for detection of antibodies to daratumumab and rHuPH20. A listing of any subjects positive for antibodies to daratumumab and rHuPH20 will also be presented.

Pharmacokinetic/Pharmacodynamic Analyses

If sufficient data are available, then other pharmacokinetic/pharmacodynamic modeling may be performed, including exploring the relationship between serum concentrations of daratumumab and endpoints of clinical efficacy. If performed, details and results of the analysis will be presented in a separate report.

10.4 DESCRIPTION OF STATISTICAL METHODS

10.4.1 General Approach

All data collected in this study will be listed and summarized as appropriate as described below. Data from all sites will be pooled and summarized.

Continuous data will be summarized by mean, standard deviation (SD), median, first and third quartiles, and minimum and maximum. Categorical data will be presented by absolute and relative frequencies (n and %) or contingency tables.

One-sided alpha level 0.025 will be used for the primary endpoint, PFS. Hierarchical testing of secondary endpoints will be specified in the Statistical Analysis Plan (SAP) to strongly control the family-wise Type I error rate at one-sided alpha of 0.025.

10.4.2 Analysis of the Primary Efficacy Endpoint(s)

The efficacy analysis will be performed based on the ITT analysis set.

Progression Free Survival (PFS)

Progression free survival is defined as the time, in months, from the date of randomization to the date of the first documented disease progression or death due to any cause, whichever comes first. Clinical deterioration will not be considered progression. For subjects who neither progress nor die, the PFS time will be censored at the date of their last adequate disease assessment. For subjects who start a new anti-MM treatment, PFS time will be censored at the date of last adequate assessment before the start of the new treatment. For a randomized subject who does not have any post-baseline disease assessments and who has not died, PFS time will be censored at the randomization date.

Progression free survival will be compared between treatment groups using a stratified log-rank test with a one-sided $\alpha = 0.025$ level. The distribution of PFS for each treatment group will be estimated using the Kaplan-Meier product-limit method. Median and two-sided CIs for median PFS will be computed by treatment group. Kaplan-Meier plots of PFS will be presented.

A stratified Cox proportional hazard model for PFS with treatment arm as single factor will be used to estimate the HR of DaraPomDex to PomDex and its corresponding 95% CI. The stratification factor will be the same as that used in the randomization process.

Absolute frequencies and proportions of subject with disease progression or all-cause death will also be provided.

A sensitivity analysis of PFS may be conducted by excluding those subjects who already began treatment with Dara IV prior to Amendment 1.

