Approximately 302 subjects will be randomized in a 1:1 ratio to receive either daratumumab + pomalidomide + dexamethasone (DaraPomDex) or pomalidomide + dexamethasone (PomDex). Subjects who already began treatment with Dara IV prior to Amendment 1 will have the option to switch to subcutaneous administration of daratumumab for the remainder of their participation in the study and they will be counted toward the total of 302 subjects. Treatment cycles have a duration of 28 days. Subjects will receive treatment until disease progression or unacceptable toxicity. Drug administration and follow-up visits will occur more frequently for early cycles (eg, weekly or bi-weekly).

Assessment of myeloma response and disease progression will be conducted in accordance with the modified International Myeloma Working Group (IMWG) response criteria. Disease evaluations will occur monthly and consist primarily of measurements of myeloma proteins. Other measures may include bone marrow examinations, skeletal surveys, assessment of extramedullary plasmacytomas, and measurements of serum calcium corrected for albumin. Survival status, subsequent anti-myeloma treatment data, and patient reported outcome (PRO) measures will continue to be collected post-treatment.

Objectives: The primary objective of this study is to compare progression free survival (PFS) between treatment arms.

The secondary objectives are the following:

- To compare Overall Response Rates (ORR) between treatment arms
- To compare Duration of Response (DoR) between treatment arms
- To compare time to next therapy between treatment arms

- To compare Overall Survival (OS) between treatment arms
- To assess the safety and tolerability of the investigational combination treatment
- To assess the depth of response by analysis of minimal residual disease (MRD) rate for subjects with complete response (CR/sCR) and for subjects with suspected CR/sCR
- To compare health-related quality of life (HRQoL) and health utility between treatment arms
- To evaluate the immunomodulatory effects of daratumumab on T cells
- To evaluate daratumumab pharmacokinetics and immunogenicity and the immunogenicity of rHuPH20

Endpoints:

Primary endpoint: Progression free survival

Secondary Endpoints:

- ORR
- Very good partial response (VGPR) or better rate
- CR or better rate
- MRD negativity rate
- Time to response
- DoR
- Time to next therapy
- OS
- Safety (adverse events)

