4 STUDY DESIGN AND ENDPOINTS

4.1 DESCRIPTION OF THE STUDY DESIGN

This is a multicenter, Phase 3, randomized, open-label study comparing daratumumab, pomalidomide and low-dose dexamethasone (DaraPomDex) with pomalidomide and low-dose dexamethasone (PomDex) in subjects with relapsed or refractory MM who have received at least 1 prior treatment regimen with both lenalidomide and a PI and have demonstrated disease progression. The original design of this study was to treat subjects with daratumumab for IV infusion (Dara IV); however, as of Protocol Amendment 1, all new subjects will now be dosed subcutaneously with daratumumab co-formulated with recombinant human hyaluronidase rHuPH20 (Dara SC). Subjects who already began treatment with Dara IV (ie, prior to Amendment 1) will have the option to switch to Dara SC on Day 1 of any cycle starting with Cycle 3 or later. It is to be noted that throughout this document, text was added to highlight any differences between Dara IV and Dara SC dosing; and where there is no clarification, it is implied that the descriptions are the same for both Dara IV and Dara SC.

Approximately 302 subjects will be randomized in a 1:1 ratio to receive either daratumumab + pomalidomide + dexamethasone (DaraPomDex) or pomalidomide + dexamethasone (PomDex). Subjects who already began treatment with Dara IV prior to Amendment 1 will be allowed to switch to subcutaneous administration of daratumumab on Day 1 of any cycle starting with Cycle 3 or later for the remainder of their participation in the study, and they will be counted toward the total of 302 subjects. Treatment cycles have a duration of 28 days.

Pomalidomide will be administered at full dose of 4 mg orally (PO) on Days 1 through 21 of each 28-day cycle.

Daratumumab will be given at a dose of 16 mg/kg administered as an IV infusion (Dara IV) or 1800 mg subcutaneously (Dara SC) at weekly intervals (QW) for 8 weeks, then every 2 weeks (Q2W) for an additional 16 weeks, then every 4 weeks (Q4W) thereafter. Subjects will receive pre-infusion medications before infusions to mitigate potential IRRs.

Dexamethasone will be administered according to standard clinical practice and at a recommended total dose of 40 mg weekly for both treatment groups (20 mg weekly for subjects ≥ 75 years of age).

Subjects will receive treatment until disease progression or unacceptable toxicity.

[figure not shown]

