6.2 STUDY TREATMENT ACCOUNTABILITY PROCEDURES

The investigator, or a pharmacist or other appropriate individual who is designated by the investigator, will maintain accurate records of the product's delivery to the study site, the inventory at the site, the use by each subject, and the return to the Sponsor or alternative disposition of unused product(s). Monitoring of drug accountability will be performed by the field monitor during the study conduct and a copy of the final drug accountability and reconciliation log will be provided by the investigator(s) at the completion of the study.

Daratumumab will be administered by qualified staff and the details of each administration will be recorded in the electronic case report form (eCRF).

A diary will be used to assess compliance with the administration of pomalidomide and dexamethasone.

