10.4.3 Analysis of the Secondary Endpoint(s)

All secondary efficacy analyses will be performed based on the ITT analysis set.

Overall Response Rate (ORR)

Overall response rate is defined as the proportion of randomized subjects who achieve a best response of PR or better using modified IMWG criteria ([Appendix 2](#)).

Overall response rate will be compared between arms using a stratified Cochran Mantel-Haenszel (CMH) chi-square test with a two-sided $\alpha = 0.05$ level. The response rate, along with its exact two-sided 95% CI, will be computed within each treatment group. A two-sided 95% CI for difference of response rate between the treatment groups will also be computed.

A sensitivity analysis of ORR may be conducted by excluding those subjects who already began treatment with Dara IV prior to Amendment 1.

Very Good Partial Response (VGPR) or Better Rate, CR or Better Rate, MRD Negativity Rate

Very good partial response (VGPR) or better rate is defined as the proportion of randomized subjects who achieve a best response of VGPR or better using modified IMWG criteria.

Complete response (CR) or better rate is defined as the proportion of randomized subjects who achieve a best response of CR or better using modified IMWG criteria.

Minimal residual disease (MRD) negativity rate is defined as the proportion of randomized subjects who achieve a negative result of MRD. Subjects without MRD assessment will be considered as having MRD-positive results.

These categorical endpoints will be analyzed similarly to ORR.

Time to Response

Time to response is defined for subjects who achieve a confirmed response as the time between the date of randomization and the first efficacy evaluation that the subject has met all criteria for PR or better.

Descriptive statistics will be used to summarize time to response.

Duration of Response (DoR)

Duration of response will be restricted to the randomized subjects who achieve a best response of PR or better. It is measured from the time, in months, that the criteria for response are first met until the date of a progression event (according to the primary definition of PFS). A subject with response who does not have a progression event will be censored at the same time they were censored under the primary definition of PFS.

The DoR for each treatment group will be estimated descriptively using the Kaplan-Meier product-limit method.

Time to Next Therapy

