10.4.8 Additional Sub-group Analyses

Additional sub-group analyses will be detailed in the SAP.

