10.6 MEASURES TO MINIMIZE BIAS

10.6.1 Enrollment/ Randomization/ Masking Procedures

Subject Numbering

Each subject is identified in the study by a Subject Number (Subject No.), that is assigned when the subject is first enrolled for screening and is retained as the primary identifier for the subject throughout his/her entire participation in the study. The investigator or designated staff will contact the Interactive Web Response System (IWRS) and provide the requested information for the subject to register them into the system. Once assigned, the Subject No. must not be reused for any other subject and the Subject No. for that individual must not be changed. If the subject fails to be randomized for any reason, then the reason will be entered into the Screening Disposition page.

Treatment Assignment/Randomization

Subjects will be assigned to 1 of the treatments (ie, DaraPomDex vs. PomDex) in a 1:1 ratio stratified by number of lines of prior therapy (1 vs. 2-3 vs. ≥ 4) and ISS stage (1, 2, 3). Subjects who already began treatment with daratumumab for IV infusion (Dara IV) prior to Amendment 1 approval will be offered the option to switch to SC dosing through study end, and they will be counted toward a total of 302 subjects.

The randomization numbers will be generated using procedures that ensure that treatment assignment is unbiased. A subject randomization list will be produced by the IWRS provider using a validated system that automates the random assignment of subject numbers to randomization numbers. These randomization numbers are linked to the different treatment arms, which in turn are linked to medication numbers.

Prior to dosing, all subject who fulfill all inclusion/exclusion criteria will be randomized via IWRS to 1 of the treatment arms. The investigator or his/her delegate will log on to the IWRS and confirm that the subject fulfills all the inclusion/exclusion criteria. The IWRS will assign a randomization number to the subject, which will be used to link the subject to a treatment arm and will specify a unique medication number for the first package of study treatment to be dispensed to the subject.

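### The optional PFS and ORR sensitivity analyses remove Dara IV starters from the DaraPomDex arm only, so early PomDex subjects are left without concurrently randomised comparators

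*Combined protocol and SAP*

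**What the plan says.** Section 4.1 describes a 1:1 comparison of DaraPomDex with PomDex. Daratumumab was first given intravenously, and "as of Protocol Amendment 1, all new subjects will now be dosed subcutaneously with daratumumab". Subjects who had already started IV could switch later, and Section 10.3 says of them that "they will be included as part of the ITT population".

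Two optional sensitivity analyses address these subjects. For PFS (Section 10.4.2): "A sensitivity analysis of PFS may be conducted by excluding those subjects who already began treatment with Dara IV prior to Amendment 1". For ORR (Section 10.4.3): "A sensitivity analysis of ORR may be conducted by excluding those subjects who already began treatment with Dara IV prior to Amendment 1". Neither section mentions PomDex subjects randomised in the IV period.

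Section 10.6.1 allocates subjects "in a 1:1 ratio stratified by number of lines of prior therapy" and by ISS stage. The PFS model in Section 10.4.2 has treatment as its only factor, with the randomisation strata. ORR uses a stratified CMH test.

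Section 10.4.8 states: "Additional sub-group analyses will be detailed in the SAP". Section 10.4.10 defers additional exploratory analyses in the same way. The document reviewed contains no SAP text.

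**The concern.** The exclusion depends on having started IV daratumumab, which happens after randomisation and can happen in one arm only. Applying it takes the early subjects out of DaraPomDex and keeps the early PomDex subjects. If k subjects started IV, about k of the 151 PomDex subjects were randomised in the same period and lose their concurrent comparators. They are then compared with DaraPomDex subjects enrolled later, and that part of the comparison is no longer randomised.

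The rule can be applied in practice: for daratumumab, Section 6.2 says "the details of each administration will be recorded in the electronic case report form", so IV starters are identifiable. The fault is that it is one-sided.

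If subjects or assessments changed between the periods in ways that prior lines and ISS do not capture, the estimate moves in a direction that depends on the sign of the change. A reader could take a difference from the ITT result as an IV-versus-SC effect, or a real one could be masked.

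**Working it through.** **Design figures first.** Section 10.5 gives HR 0.621, one-sided alpha 0.025, 90% power, 188 events and 302 subjects (151 per arm). Schoenfeld's formula gives 186 events and Freedman's 193; power at 188 events is 90.4%; 280/0.93 = 301.1, so 302 for equal arms. The plan's figures reproduce and are not in dispute.

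**Assumptions.** The documents do not state k or any drift. The original protocol (7 April 2017) and Amendment 1 (13 October 2017) were issued 189 days, or 6.2 months, apart. That interval includes start-up, although local approval could lengthen the IV period. I take k = 5 to 50, with 50 as an upper scenario, and an early/late hazard ratio of 0.67 to 1.5 acting outside the strata.

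**Bias in the HR.** A large-sample stratified Cox simulation was run with 1,000,000 subjects per arm, exponential PFS, true HR 0.621 and early share k/151. Further assumptions were a control median of 7 months in the lower-risk stratum, censoring at 24 months, and one binary stratum with HR 2 and later-period prevalence 0.4.

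**Precision.** Events d = 188 × (subjects kept)/302; p = DaraPomDex share of those kept; SE = 1/√(d·p·(1−p)).
- k=10, one arm: d = 188 × 292/302 = 181.8, p = 141/292 = 0.483, SE = 0.148. Both arms: d = 188 × 282/302 = 175.5, p = 0.5, SE = 0.151.
- k=50, one arm: d = 188 × 252/302 = 156.9, p = 101/252 = 0.401, SE = 0.163. Both arms: d = 188 × 202/302 = 125.7, SE = 0.178.

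Largest shift in SE units = ln(HR/0.621)/SE. For k=50: ln(0.720/0.621)/0.163 = 0.148/0.163 = 0.91. Power = Φ(|ln 0.621|/SE − 1.96), with |ln 0.621| = 0.476.

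| k | PomDex unmatched (k/151) | One-arm HR, drift 0.67 / 1.0 / 1.5 | Largest shift (SE) | Power, one-arm vs both-arm |
|---|---|---|---|---|
| 5 | 3% | 0.630 / 0.620 / 0.615 | 0.10 | 90% vs 89% |
| 10 | 7% | 0.639 / 0.622 / 0.608 | 0.19 | 89% vs 88% |
| 15 | 10% | 0.651 / 0.621 / 0.600 | 0.31 | 89% vs 87% |
| 30 | 20% | 0.677 / 0.620 / 0.580 | 0.56 | 87% vs 83% |
| 50 | 33% | 0.720 / 0.623 / 0.555 | 0.91 | 83% vs 76% |

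Both-arm exclusion gave 0.620 to 0.623 in every scenario. A simpler unstratified simulation (control median 6 months, censoring at 18) agreed: 0.65/0.60 at k=15 and 0.67/0.58 at k=30.

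**When the bias shrinks or vanishes.** With half the drift carried by the strata, the one-arm HR is 0.630/0.614 at k=10 and 0.662/0.585 at k=50. With drift wholly inside the strata it is 0.620 to 0.621. With a difference only in follow-up length (early/late censoring 36/24, 36/12 or 24/12 months) it is 0.620 to 0.622.

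**ORR.** Take 31% (pomalidomide plus low-dose dexamethasone, Section 2.2) and 59% (DaraPomDex in MMY1001, Section 2.1.2) as assumed later-period rates, a difference of 28.0 points. PomDex odds are 0.31/0.69 = 0.449. Multiplied by 1.5 or 0.67, they give early rates of 40.3% or 23.1%.
- k=10: PomDex rate = 31 + (10/151)(40.3 − 31) = 31.6%, or 30.5% at the other extreme; difference 27.4 to 28.5 points.
- k=50: PomDex rate = 34.1% or 28.4%; difference 24.9 to 30.6 points.

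**The case against.** Nothing confirmatory depends on these analyses. Both are optional, and the primary and secondary efficacy analyses are ITT and keep the IV starters. Harm needs both a non-trivial k and drift outside the strata, and the documents give neither. The protocol also leaves statistical detail to a SAP that is not in the document reviewed, and that SAP could define the exclusion in both arms. All of this stands and limits the severity. However, Sections 10.4.8 and 10.4.10 defer additional subgroup and exploratory analyses, not this sensitivity set, so the deferral does not clearly cover it.

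The strongest technical point concerns mean squared error. For small k, keeping every PomDex subject gains about as much precision as it costs in bias. At k=10 with drift 0.67, the one-arm value for the log HR is 0.1484² + 0.0286² = 0.0228, and the both-arm value is 0.1509² = 0.0228. With milder drift the one-arm rule is slightly better. At k=50 with drift 0.67 the order reverses: 0.163² + 0.148² = 0.048 against 0.178² = 0.032. So there is a near-tie at small k, but that does not make the one-arm set a randomised comparison.

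The risk of misreading the result as a route effect is an inference, because no section gives route comparison as the purpose. Finally, the primary cutoff (21 July 2020, Table 7.3) has passed, so a rewording now cannot make the analysis prespecified.

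**Conclusion.** The concern holds for the protocol wording. The rule can only remove DaraPomDex subjects, nothing in the document removes their PomDex contemporaries, and the stratified methods do not adjust for period. A DaraPomDex subject randomised early but never started on IV would stay in, so a few concurrent comparators could remain.

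The size depends on assumed k and drift. If about 10 subjects started on IV, the shift is at most about 0.2 SE of the log HR. It reaches 0.9 SE only if about 50 did and the drift is at the assumed extreme, and it is zero without drift outside the strata. The ITT results, alpha, sample size and interim analysis are untouched. This is a minor, optional improvement. Confidence is high about what the protocol says, and does not extend to an unseen SAP.

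**What to change.** In Sections 10.4.2 and 10.4.3, define the sensitivity set by randomisation date: exclude every subject, in both arms, randomised before their site moved to Dara SC under the approved Amendment 1. Keep the stratified log-rank, Cox and CMH methods. Because the primary cutoff has passed, report the both-arm version as post hoc, and label any one-arm result as a non-randomised comparison.

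The cost is one sentence in each section plus the site switch dates. Those dates are needed because Section 13.2 requires ethics committee and/or authority approval before an amendment is implemented; the documents do not list them as collected data. Early PomDex subjects also leave the set. Relative to the one-arm rule, the CI for the log HR is about 2% wider at k=10 (0.151/0.148) and about 10% wider at k=50 (0.178/0.163). At k=50 about 126 events remain instead of 157.
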